2.2 Secondary Objective

Time it takes to apply each respective treatment (APC or STSC)

Number of complications for each randomization arm. Examples include bleeding, perforation, pain or post polypectomy syndrome.

Cost analysis detailing the effectiveness of the treatment versus the cost of each therapeutic device (argon probe vs. snare).

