3.2 Secondary Outcome Measures

Time it takes to apply each treatment will be recorded by a research assistant during the index procedure using a stop watch. During the colonoscopy the

treatment time will be recorded as the time, after initial polyp resection, that the randomized treatment instrument comes into view until before clips are applied. Complications will be assessed during the follow-up call simply by asking the patients if they experienced any adverse events. We will use the following definitions to ascertain complications:

Bleeding: severe bleeding event that required hospitalization, a blood transfusion, a colonoscopy, surgery, or any other invasive intervention to control bleeding, and that occurred after the patient left the endoscopy unit and within 30 days after completion of the colonoscopy

Perforation: iatrogenic full thickness defect in the colon wall diagnosed within two weeks of the procedure

Pain: Any pain perceived by the patient after they left the endoscopy unit and within 30 days after completion of the colonoscopy

Post polypectomy syndrome: Abdominal pain, fever, leukocytosis and peritoneal inflammation in the absence of perforation within two weeks of the procedure

Our cost analysis will then take all of these endpoints into account to report which method we found to be more affective. As stated, this will be based on the instrument cost, treatment time, polyp recurrence, and reported complications.

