9.0 Data Safety Monitoring

See Data and Safety Monitoring Board Charter for information about DSMB. Briefly, the data safety monitoring board comprises 4 members: [name] MD (Indiana University), [name] PhD (Indiana University), [name] MD (Henry Ford Hospital), and [name] MD (Chair), (Medical University of South Carolina). None of the board members are involved with the current study in any capacity. Additionally, [name] research team will provide him up to date information regarding the status of patients and any reportable events.

The data collected at sites other than IU will be de-identified before being sent to us. Each site will enter their data in to a secure web application (REDCap), which will then be accessed at the primary site. Only de-identified data from external sites will be added to the database (no HIPAA identifiers will be collected from external sites besides procedure dates and de-identified images of study lesions). Any other communication that is not patient related will be done over email or phone.

Variables that will be transmitted from the other site include:

- Information from the procedure to remove the large polyp
 - This includes information about meeting inclusion/exclusion criteria, procedure date, randomization envelope number/randomization treatment, age, gender, race,

ethnicity, whether a fellow was involved in the procedure (and which parts of procedure, if applicable), procedure times, study polyp characteristics, de-identified study lesion images, resection times, information about the resection such as snare/ injection fluid usage and number of resected pieces, treatment times, other additional treatments used, clipping times, number/type of clips used, type of colonoscope used, Boston Bowel Preparation Score, whether fibrosis was present, whether there were any prior attempts at resection, information about procedural complications (if any), and study polyp pathology results

- Information from the 30 day follow up call
 - This includes information about whether the follow-up phone call was made successfully, date subject was reached by phone, and whether patient reported experiencing adverse events (and if so, information about the adverse event).
 - Information from the first follow-up procedure

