11.0 Statistical Considerations

Assuming a 25% recurrence rate of the control arm, and a reduction to 10% in both of the treatment arms, we estimate that a sample size of 115 subjects per arm will be needed to demonstrate that APC and STSC are superior to no treatment for reduction of recurrence rate after EMR, based on 80% power and a two-sided 5% significance level for comparison of independent proportions with one interim analysis. The no treatment arm will be used as our control. In order to account for drop-outs, an extra 35 patients will be enrolled into the study to ensure sufficient data will be included in the analysis. Therefore, a sample size of 380 subjects will be enrolled in this study.

Once a polyp has been identified and its size fits within the targeted range, each subject will be randomized in a 1:1:1 ratio using a computer generated randomization sequence. Enrollment into the study will be competitive with the possibility for each site outside of IU to randomize up to 100 patients. Not all 645 randomization numbers generated will be used in the study. Instead each external site will continue to enroll until a total of 380 patients have been randomized study-wide with a potential to randomize up to 100 patients. Randomization numbers will be assigned as follows: IU will be assigned numbers 001 – 095 and 496 - 526; AdventHealth Orlando will be assigned 096 – 145 and 446 - 470; The Johns Hopkins Hospital will be assigned numbers 146 – 195; Dartmouth-Hitchcock Medical Center will be assigned numbers 196 – 245; NYU Langone Medical Center will assigned numbers 246 – 295 and 471 - 495; the Mount Sinai

Hospital will be assigned 296 – 345, Sibley Memorial Hospital will be assigned 346 – 395, the University of Kansas Medical Center will be assigned 396 – 445, and Penn State Health Milton S. Hershey Medical Center will be assigned 546 - 595. The proportion of subjects with recurrence will be compared between study arms using chi-square tests. The number of complications will be compared among treatment arms using negative binomial regression. Treatment times and costs will be compared between the APC and STSC arms using Wilcoxon Rank Sum tests. A 5% significance level will be used for all tests.

Interim analysis and stopping rule:

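### The only specified complication comparison adds any pain to severe bleeding, perforation and post polypectomy syndrome, so its one result cannot show which of them changed

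*Combined protocol and SAP*

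**What the plan says.** Section 2.2 sets the secondary objective as "Number of complications for each randomization arm" and adds "Examples include bleeding, perforation, pain or post polypectomy syndrome".

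Section 3.2 then defines the four types, with unequal thresholds:
- Bleeding must be a "severe bleeding event that required hospitalization, a blood transfusion, a colonoscopy, surgery, or any other invasive intervention to control bleeding".
- Pain has no threshold: "Pain: Any pain perceived by the patient after they left the endoscopy unit and within 30 days after completion of the colonoscopy".
- Perforation is a full-thickness defect found within two weeks.
- The syndrome itself contains pain: "Post polypectomy syndrome: Abdominal pain, fever, leukocytosis and peritoneal inflammation in the absence of perforation within two weeks of the procedure".

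Section 11.0 gives one analysis for all of this: "The number of complications will be compared among treatment arms using negative binomial regression". It is tested at 5%. The documents give no weights, hierarchy, analysis by type, or rule for counting overlapping events.

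Section 9.0 shows that the raw material exists. The 30-day call records "whether patient reported experiencing adverse events (and if so, information about the adverse event", and procedural complications are recorded at the index colonoscopy.

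**The concern.** The trial adds thermal treatment to the resection margin in two arms and nothing in the third. Readers will ask two separate safety questions: does the added treatment change bleeding, perforation or post polypectomy syndrome, and does it change pain? A single test on the sum answers neither.

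If pain is common and similar across arms, it can dilute a rise in the other three. If pain differs, a significant result may be pain alone. Section 3.2 also uses reported complications as an input to the cost analysis.

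A smaller matter is that abdominal pain is part of the definition of post polypectomy syndrome. One episode could be scored once or twice, and the plan does not say which.

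**Working it through.** **Inputs.** The plan states no complication figure to reproduce. The 115 per arm in section 11.0 belongs to the primary comparison. It is consistent with the continuity-corrected two-proportion formula for 25% v 10% at 80% power, which gives 113 at alpha 0.05 and 114 at 0.049. The enrolment total is 3 × 115 + 35 = 380. Complications are collected at 30 days or, failing that, at the first follow-up colonoscopy (section 7.0). The safety sample could therefore reach 380 / 3, about 126 per arm, and both sizes are used below. All event rates are assumed. *The three* means bleeding, perforation or post polypectomy syndrome; this grouping is mine, not the plan's.

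**Step 1: the sum cannot be separated.** With pain rate p and rate s for the three, the modelled ratio is (p_T + s_T) / (p_C + s_C).
- Only pain rises: (0.26 + 0.03) / (0.20 + 0.03) = 1.26.
- Only the three rise: (0.20 + 0.09) / (0.20 + 0.03) = 1.26.
- The three triple while pain falls: (0.14 + 0.09) / (0.20 + 0.03) = 1.00.

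These rates only illustrate the point. The algebra holds for any rates.

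**Step 2: dilution when pain is equal.** Take the three at 3% v 9%, pain 30% in both arms and independent of the three, n = 115.
- Means: 0.33 and 0.39, so the log ratio is ln(0.39/0.33) = 0.167.
- Variances p(1−p) + s(1−s): 0.210 + 0.0291 = 0.2391 and 0.210 + 0.0819 = 0.2919.
- Robust SE: √[(0.2391/0.33² + 0.2919/0.39²)/115] = √(4.115/115) = 0.189.
- z = 0.167/0.189 = 0.88, and power = Φ(0.88 − 1.96) + Φ(−0.88 − 1.96), about 14%.

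The same steps with pain at 10% give ln(0.19/0.13) = 0.379, SE 0.320, z = 1.18 and power of about 22%. Simulation gives 21%.

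**Step 3: part of the loss comes from the model.** The control variance in step 2, 0.2391, is below its mean of 0.33, so the counts are underdispersed. A negative binomial model cannot go below Poisson variance. Its SE is therefore about √[(1/0.33 + 1/0.39)/115] = 0.221 rather than 0.189, and its test is conservative. With no true difference and 30% pain it rejects in about 2% of trials.

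**Step 4: results for the three at 3% v 9%, equal pain.**

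| Analysis | Pain 10% | Pain 30% |
|---|---|---|
| Pooled count, model-based errors (115 per arm) | 18% | 8% |
| Pooled count, robust errors (115 to 126) | 21-22% | 14-15% |
| Fisher's exact test on the three alone (115 to 126) | 36-41% | 36-41% |

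**Step 5: pain alone drives the result.** With the three at 3% in both arms and pain 10% v 20%, the pooled test is significant in about 41-50% of trials, depending on the errors used and the sample size. Fisher's test on the three is significant in 1.4% (115 per arm).

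**Step 6: where pooling does not lose (115 per arm, model-based).**
- The three at 3% v 9% with pain 10% v 15%: pooled 48%. With pain 30% v 40%: pooled 46%. Fisher 36-37%.
- Every one of the three also scored as pain, pain 5%: pooled 37%, Fisher 36%.
- A doubling, 3% v 6%, with equal pain of 10% / 30%: pooled 7% / 4%, Fisher 11%.

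**Step 7: the counting rule.** With pain 30%, the three at 3% v 9% and model-based errors, scoring the syndrome's own pain once or twice gives 7% v 9% power if the syndrome makes up 10% of the three, and 5% v 14% if it makes up half.

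**The case against.** The strongest reply is that nothing says the types must be summed. Section 2.2 offers them as examples, and section 3.2 defines each separately with its own window. Event details are collected, a safety board with its own charter exists, and tables by type are routine. That stands in part. The sum is an inference, though an unqualified number in a count model leaves little other reading. The charter was not available, so review by type can be neither assumed nor ruled out. What is missing is a specified breakdown, not the data to make one.

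A reader might infer that the trial will hide a rise in serious complications. The documents do not support that: they give no rates and do not prevent reporting by type.

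A reader might also infer that pooling always costs power. Step 6 shows that it does not. The power gap under the model-based test also overstates dilution, because part of it is the conservatism shown in step 3.

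Finally, a composite of the three again pools unlike events, so a test on it would not show which one changed. That objection stands in full, and it is why estimates by type are the core of the fix.

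**Conclusion.** The point holds as a modest one about a secondary endpoint for which the trial was not sized. The one specified complication result cannot separate pain from the other three types. That follows from the structure of the analysis and needs no assumed rate, only the reading that the types are summed.

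The size does rest on assumed rates, on independence of pain from the other events except where stated, and on 115 to 126 patients per arm. Under those assumptions, power to see a tripling of the three falls from 36-41% to about 21-22% or 14-15% with robust errors, for pain of 10% or 30%. Other plausible assumptions reverse the direction. For a doubling, sample size is the main limit whichever analysis is used.

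**What to change.** Add to section 11.0:

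> Each complication type (bleeding, perforation, post polypectomy syndrome, pain) will be reported as the number and proportion of patients by arm, with risk differences v control and 95% CIs. Pain that is part of another defined complication is not counted again. The total count is a supporting analysis, with robust standard errors.

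Optionally, the proportion of patients with at least one of the three complications other than pain may be compared with control by Fisher's exact test. The grouping is a reviewer's choice and the test is not essential.

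The cost is three sentences and a few more safety tables, with no new data. Intervals for rare events will be wide. With 3/115 in both arms, the Wilson limits for each proportion are 0.9% and 7.4% around 2.6%. The Newcombe interval for the difference is then ±√(1.72² + 4.78²) = ±5.1 percentage points. A non-significant result would not be evidence of safety under this plan either, and the report should say so.

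### Negative binomial regression for complications loses power to show harm if pain is common and mostly one event per patient; robust Poisson regression covers either case

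*Combined protocol and SAP*

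**What the plan says.** Section 2.2 names the outcome as a count with an open list of types: "Number of complications for each randomization arm. Examples include bleeding, perforation, pain or post polypectomy syndrome". Section 3.2 defines the four types. Bleeding is limited to serious events: "Bleeding: severe bleeding event that required hospitalization, a blood transfusion, a colonoscopy, surgery, or any other invasive intervention to control bleeding". Perforation is a full-thickness defect found within two weeks. Pain is broad: "Pain: Any pain perceived by the patient after they left the endoscopy unit and within 30 days after completion of the colonoscopy". Post polypectomy syndrome is defined as "Abdominal pain, fever, leukocytosis and peritoneal inflammation in the absence of perforation within two weeks of the procedure", so a patient with it would normally also meet the pain definition. Ascertainment is by telephone: "Complications will be assessed during the follow-up call simply by asking the patients if they experienced any adverse events".

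The inference is one sentence in section 11.0: "The number of complications will be compared among treatment arms using negative binomial regression". The level is set by "A 5% significance level will be used for all tests". The documents give no expected complication rate, no rule for counting overlapping types, no form of test (Wald or likelihood ratio), and no fallback if the model does not fit.

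**The concern.** Negative binomial regression is designed for counts whose variance exceeds the mean. Its variance is mean + dispersion × mean², with dispersion at or above zero, so it never falls below the mean. A yes/no event with probability p has variance p(1 − p), which is below its mean p. If most patients score 0 or 1 and the 1s are mainly pain, the dispersion estimate goes to zero, the model becomes ordinary Poisson regression, and its standard errors are too wide.

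For a safety comparison this is the unhelpful direction of error: a real excess of complications with APC or STSC would be less likely to show. Complications also feed the cost analysis described in section 3.2.

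**Working it through.** **Inputs from the documents.** The 115 per arm is a figure for recurrence; the continuity-corrected two-proportion formula gives 113 to 114, close to it. Then 3 × 115 + 35 = 380, allocated 1:1:1, and 380/3 = 126.7. I use n = 126 per arm. The plan has no figure of its own for the complication test.

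**Assumptions (not in the documents).** Bleeding 3%, perforation 0.5%, post polypectomy syndrome 0.5% and always accompanied by pain. Bleeding and perforation are independent of pain. Pain rate p is varied.

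**Step 1: dispersion.**
- Mean = p + 0.03 + 0.005 + 0.005 = p + 0.04.
- Variance = p(1 − p) + 0.03×0.97 + 2×0.005×0.995 + 2×0.005×(1 − p). The last term is the overlap of the syndrome with pain.
- When the variance is below the mean, the standard error is too wide by the factor 1/√(variance/mean), and the actual two-sided error at nominal 5% is 2Φ(−1.96/√(variance/mean)).

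| Pain | Mean | Variance | Variance/mean | SE too wide by | Actual type I error |
|---|---|---|---|---|---|
| 2% | 0.06 | 0.068 | 1.14 | not applicable | not applicable |
| 5% | 0.09 | 0.096 | 1.07 | not applicable | not applicable |
| 10% | 0.14 | 0.138 | 0.99 | 1% | 4.8% |
| 20% | 0.24 | 0.207 | 0.86 | 8% | 3.5% |
| 30% | 0.34 | 0.256 | 0.75 | 15% | 2.4% |

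Setting variance equal to mean gives p² + 0.01p − 0.00905 = 0, so p ≈ 9%. Below that pain rate the count is over-dispersed even in this model. In the limiting case where every count is 0 or 1, the factor is 1/√(1 − p): 5% at a rate of 10%, 12% at 20%, 20% at 30%.

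**Step 2: power, one active arm against control, only pain differing.** Let d = ln(mean₁/mean₀). Poisson SE = √[(1/mean₀ + 1/mean₁)/n]. True SE = √[(f₀/mean₀ + f₁/mean₁)/n], where f is variance/mean. Poisson-limit power = Φ[(d − 1.96×Poisson SE)/true SE]. Robust power = Φ(d/true SE − 1.96).

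| Pain, control v active | d | Poisson SE | True SE | Power, Poisson limit | Power, robust |
|---|---|---|---|---|---|
| 5% v 13% | 0.636 | 0.367 | 0.372 | 41% | 40% |
| 10% v 20% | 0.539 | 0.300 | 0.291 | 43% | 46% |
| 20% v 33% | 0.433 | 0.233 | 0.210 | 45% | 54% |
| 30% v 45% | 0.365 | 0.199 | 0.165 | 44% | 60% |

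The Poisson SE exceeds the true SE by 11% in the third row and 20% in the fourth. Simulations with the dispersion estimated agree: 43% to 47% against 54% to 55% for 20% v 33%, and 41% to 46% against 59% to 62% for 30% v 45%.

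**Step 3: overlap.** Suppose 60% of patients with bleeding or perforation also report pain, with overall pain held at p. This adds 2×0.035×(0.6 − p) to the variance. Variance/mean becomes 1.50 at 5% pain, 1.24 at 10%, 0.98 at 20% and 0.81 at 30%. Heavy overlap therefore removes the problem up to about 20% pain, but not at 30%.

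**The case against.** The strongest reply is that the documents never say the count is 0/1. Section 2.2 calls it a number and gives the four types only as examples. Nothing caps a patient at one event, and the syndrome and pain definitions overlap. For such a count negative binomial regression is a conventional choice, and with rarer pain or heavy overlap the data are over-dispersed, as the working shows. This stands. It limits the point to a conditional one, but it does not supply a reason to prefer a model that fails on one side of the range.

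A reader might go further and infer that the test is conservative by construction. The documents do not support that: they give neither a rate nor a counting rule, and the sign of the effect depends on both.

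A reader might also infer that the model will often fail to fit. When dispersion reaches its boundary, some routines do return no usable standard error, but that depends on software, which section 11.0 does not name. The Poisson limit still gives an estimate unless an arm has no events. Nor do zero counts within rare types count against the plan: it sets out one analysis of the number of complications, not one per type, and Poisson regression would have the same difficulty.

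Finally, replacing the count by the proportion with any complication would change the question asked, since it ignores multiple events and treats mild pain like perforation. That is a fair reason to keep the count as the main complication analysis.

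**Conclusion.** The point holds conditionally. If pain is at about 20% or more with limited overlap between types, standard errors are about 8% to 20% too wide, type I error falls to roughly 2% to 4%, and power to detect more harm is roughly 10 to 18 points below that of an analysis with the correct variance. At 10% v 20% pain the loss is about 3 points, and at 5% v 13% there is none. All of these rates are assumptions. The mechanism is certain; its size in this trial cannot be known from the documents. Because this is a secondary outcome with no claimed power, the severity is minor to moderate.

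**What to change.** In section 11.0, replace negative binomial regression with Poisson regression of the per-patient number of complications on arm, using robust (sandwich) standard errors. This keeps the planned count and rate ratio and is valid under both under- and over-dispersion. In the scenarios simulated it held type I error at 3.4% to 5.4% and cost at most about 3 points of power when counts were over-dispersed.

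Add one supporting analysis: the proportion of patients with at least one complication, each active arm against control, by chi-square test (Fisher exact if sparse), with risk differences and 95% confidence intervals. This also gives a result if an arm has no events.

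It would help to state in the same place whether a patient with post polypectomy syndrome also counts under pain. The cost is two or three sentences, with no new data and no additional patients.

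### The only named cost test, a rank sum comparison of APC with STSC, does not estimate mean cost and leaves out the no-treatment arm, so it does not answer the plan's own cost question

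*Combined protocol and SAP*

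**What the plan says.** Section 2.2 (Secondary Objective) promises a "Cost analysis detailing the effectiveness of the treatment versus the cost of each therapeutic device (argon probe vs. snare"). Section 3.2 (Secondary Outcome Measures) says of the conclusion on the better method that "this will be based on the instrument cost, treatment time, polyp recurrence, and reported complications".

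The statistical method is a single sentence in section 11.0: "Treatment times and costs will be compared between the APC and STSC arms using Wilcoxon Rank Sum tests". The same section adds that "A 5% significance level will be used for all tests". It also compares recurrence between study arms by chi-square and complications among arms by negative binomial regression, and it names the no-treatment arm as the control.

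No section defines the per-patient cost variable, gives unit prices, or names an estimate of mean cost or cost-effectiveness. No cost comparison that includes the no-treatment arm is named.

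**The concern.** Whether money spent on a device is recovered through fewer recurrences or complications depends on how large those later costs are, averaged over patients. That average is the arithmetic mean cost. A rank sum test asks a different question: how often a patient in one arm costs more than a patient in the other. It registers that a patient with a recurrence is expensive, but not by how much.

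The components in section 3.2 are of the kind that pulls these two questions apart: a device price set largely by arm, plus a few large event costs. A reader could be told, with a very small p-value, that one method costs more when its mean cost is equal or lower.

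The restriction to two arms adds a second gap. Section 11.0 plans on "Assuming a 25% recurrence rate of the control arm, and a reduction to 10% in both of the treatment arms", so on the plan's own assumption APC and STSC do not differ in recurrence. All the benefit to be set against cost lies in the comparison with no treatment.

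**Working it through.** **Plan's own figure.** There is none for cost. The only figure used below is the number per arm: "a sample size of 115 subjects per arm will be needed". For 25% v 10%, the usual two-proportion formula gives

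n = [1.96 × √(2 × 0.175 × 0.825) + 0.842 × √(0.1875 + 0.09)]² / 0.15² = 1.497² / 0.0225 ≈ 100,

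and 113 to 114 with continuity correction (two-sided alpha 0.05 or 0.049). So 115 is reproduced closely, and 3 × 115 + 35 = 380.

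**Assumptions.** The documents give no prices, so every cost here is assumed, in arbitrary units: time at 10 per minute; treatment time lognormal with median 4 minutes and log-SD 0.5 in both arms; 2000 per recurrence; APC device dearer than STSC by d.

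**Mean difference (APC minus STSC)** = d + 2000 × (rA − rS), where rA and rS are the recurrence rates.

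**Standard error of the mean difference** = √{[2000² × (rA(1 − rA) + rS(1 − rS)) + 2 × 583] / 115}. Here 583 is the variance of time cost, 40² × e^0.25 × (e^0.25 − 1).

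**What the rank test sees.** When d exceeds the spread in time cost, P(APC > STSC) ≈ 1 − (1 − rA) × rS. For 5% v 20% this is 1 − 0.95 × 0.20 = 0.81. The null standard error is √(231 / (12 × 115²)) = 0.038, so the test statistic is about 0.31 / 0.038 ≈ 8. The price per recurrence does not enter.

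| d | Recurrence, APC v STSC | True mean difference | SE | Chance that the sample mean has APC cheaper (normal approximation) | Simulated: significant for APC dearer, but sample mean says cheaper |
|---|---|---|---|---|---|
| 200 | 10% v 10% | +200 | 79 | 1% | 1% |
| 50 | 10% v 10% | +50 | 79 | 26% | 27% |
| 50 | 8% v 12% | 50 − 80 = −30 | 79 | 65% | 68% |
| 200 | 5% v 20% | 200 − 300 = −100 | 85 | 88% | 89% |

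In the two unequal-rate rows, 100% of simulated trials were significant for APC dearer although APC is truly cheaper on average. In the last row a mean comparison gives about −100 ± 1.96 × 85, that is −267 to +67, which is inconclusive.

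**Complications instead of recurrence.** With d = 100, 20 per minute, 3% v 7% complications and 5000 per event, the mean difference is 100 − 0.04 × 5000 = −100. The test calls APC dearer in 100% of trials and contradicts the sample means in 72%. The SE is about 143, so a 95% interval would run from about −380 to +180.

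**Where device price is everything.** If cost is device price alone and constant within arm, any gap gives p = 0.004 with 5 per arm and about 1e-51 with 115. Rank and mean then agree in direction, but the test reports only the price list.

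**Where neither happens.** With device and time cost only (20 per minute, median 3 minutes, log-SD 0.6), the test is significant in 5% of trials at d = 0, 21% at d = 5, 60% at d = 10 and 99.9% at d = 25. At d = 50 with APC faster (median 2 v 4 minutes) it is 69%.

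**The missing arm.** Take the plan's rates (25% v 10% and 10%), d = 200, STSC device cost 0 and mean time cost 40 × e^0.125 = 45.
- At 2000 per recurrence, mean costs are 500 for no treatment, 200 + 45 + 200 = 445 for APC and 45 + 200 = 245 for STSC.
- At 1500 per recurrence they are 375, 200 + 45 + 150 = 395 and 45 + 150 = 195.

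APC minus STSC is +200 both times, while APC minus no treatment moves from −55 to +20. The named comparison cannot see that change.

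**The case against.** The strongest reply is that the reversal rests on assumptions away from the plan. Section 11.0 expects 10% recurrence in both treated arms. At those rates the true mean difference equals the price gap, rank and mean agree in direction, and contradiction with the sample mean is about 1% at a gap of 200. This stands: a true reversal needs the treated arms to differ in event rates, and event costs to be counted. Section 3.2 does count them, and the trial cannot know in advance that the rates are equal.

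A reader might infer that the test is significant by construction at any realistic sample size. The documents do not support that. They give no prices, section 3.2 includes components that vary by patient, and section 11.0 names several sites, where prices may differ. That device price is nearly fixed by arm is a reasonable inference, not a stated fact.

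A reader might also infer that the plan as a whole cannot judge whether treatment is worth its cost. That too goes further than the text. Recurrence and complications are compared across arms, and nothing bars a three-arm cost summary. What holds is narrower: the one cost test named cannot show it. Limiting treatment time to APC and STSC is sensible, since the control arm has no application time; that reasoning does not carry over to total cost.

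Finally, section 2.2 contrasts the "cost of each therapeutic device (argon probe vs. snare"), while section 9.0 records "information about the resection such as snare/ injection fluid usage and number of resected pieces". It is possible that STSC would be charged for a snare already opened for the resection, but no text says so. It is an open definition, not an error.

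**Conclusion.** The mismatch between the objective and the named test stands, and so does the omission of the control arm from the cost comparison. The wrong-direction result is conditional. With the assumed prices, a significant finding of APC dearer contradicts the sample means in about 1% to 27% of trials at equal 10% recurrence, 68% with a modest difference in recurrence and a small price gap, and 89% with a large difference and a large gap. These figures illustrate the mechanism; they do not predict this trial, because prices and the cost variable are undefined. This is a secondary outcome and a cheap improvement. The primary analysis and the sample size are unaffected.

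**What to change.** Keep the Wilcoxon test for treatment time. For cost, amend section 11.0 as follows:

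- Define cost per patient from the four components in section 3.2, with stated unit prices and their source. Count as device cost only what is opened beyond the resection snare already in use.
- Report arithmetic mean cost differences per patient with bootstrap 95% confidence intervals across all three arms: APC v no treatment, STSC v no treatment, and APC v STSC.
- Set these beside the recurrence differences, for example as cost per recurrence avoided against no treatment.

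The cost is SAP wording, a short analysis and the choice of unit prices. A test of costs that draws on these components needs prices anyway, and no new patient-level data are called for. The intervals will be wider and less decisive than a rank p-value, which reflects how little a trial of this size can say about mean cost.
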